1.3 Schedule of Activities

Table 1 presents the schedule of activities for Part A prior to approval of Amendment 4. Following approval of Amendment 4, all participants in Part A will directly proceed to Visit 20 of Part D (Table 3) at their next clinic visit.

	Run-in			D.	ubla b	linded	twoat-	ont novied		In case of disc	antinuation ⁸	CSP Section
	+		ı	1	ı			nent period				CSP Section
Visit (V)	V1	V2	V3	V4	V5	V6	V7	V8 /EOT ^b	Unscheduled ^c	IP Discontinuation	Follow-up	
Week	-8 to -4	0	4	8	12	16	20	24	-	4 weeks post- dose	8 weeks post- dose	
Visit Window (Days)			± 3	± 3	± 3	± 3	± 3	± 3		± 3	± 7	
General procedures				•					-			
Informed consent/assent	X	-	-	-	-	-	-	-	-	-	-	Appendix A 3
Demography/medical history	X	-	-	-	-	-	-	-	-	-	-	-
Inclusion/exclusion criteria	X	X	-	-	-	-	-	-	-	-	-	5.1, 5.2
Height, Weight	X	-	-	-	-	-	-	X	-	X	-	8.2.1
Efficacy assessments	1	•		•	•				-			1
Provide PRO device and instructions	X	-	-	-	-	-	-	-	-	-	-	8.1.3
Site visit PRO assessments (see Table 4)	X	X	-	-	-	-	-	X	-	X	-	8.1.3
Review PRO assessment compliance	-	X	X	X	X	X	X	X	-	X	-	8.1.3
Clinical Global Impression of Severity		X	-	-	-	-	-	X	-	X	X	8.1.4
Clinical Global Impression of Change	-		X	X	X	X	X	X	-	X	X	8.1.5
Diet questionnaire	X	X	X	X	X	X	X	X	Х	X	X	8.1.6

Qualitative interview reminde	-	X	-	-	-	-	-	-	-	-	-	8.1.7
Healthcare resource utilization	-	X	X	X	X	X	X	X	-	X	X	8.8
Endoscopy: biopsy, EG- REFS, and EREFS	Xe	-	-	-	-	-	-	X	-	X ^f	-	8.1.1, 8.1.2
Safety assessments												
Adverse events	X	X	X	X	X	X	X	X	X	X	X	8.3
Concomitant medication	X	X	X	X	X	X	X	X	X	X	X	6.5
Complete/(brief) physical exam	X	(X)	(X)	(X)	(X)	(X)	(X)	X	(X)	X	(X)	8.2.1
Vital signs	X	X	X	X	X	X	X	X	X	X	-	8.2.2
Electrocardiograms	-	X	-	-	-	-	-	-	-	-	-	8.2.3
Laboratory assessments		•										·
Hematology/clinical chem	X	-	-	X	-	X	-	X	-	X	X	8.2.4
Serology (hepatitis/HIV)	X	-	-	-	-	-	-	-	-	-	-	8.2.6
Urinalysis	X	-	-	-	-	X	-	X	-	X	-	8.2.4
Post-menopause confirmation ⁱ	X	-	-	-	-	-	-	-	-	-	-	8.2.5
Serum/(urine) pregnancy	X	(X)	-	(X)	(X)	8.2.5						
Pharmacokinetics	-	X	-	X	-	X	-	X	-	X	X ^h	8.5.1
Immunogenicity	-	X	-	X	-	X	-	X	-	X	X ^h	8.5.2
Biological sampling												·
Serum for total IgE	X	-	-	-	-	-	-	-	-	-	-	8.6.1.1
Serum for tryptase	X	-	-	-	-			X				
Blood, serum, plasma for biomarkers	X	-	-	X	-	X	-	X	-	-	-	8.6.1.1
Tissue for histopathology/biomarkers	X	-	-	-	-	-	-	X	-	X ^f	-	8.6.1.2

Blood for genetic analysis	-	X^k	ı	-	-	-	-	-	-	-	-	8.7
Investigational product adm	inistration											

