^c For patients who are self-administering IP, these visits can optionally be conducted remotely by telephone contact.

d In adult participants at select sites.

To be completed at the discretion of the Sponsor and in accordance with guidance in Section 7.2.

											CSP Section
Visit (V)	V20	V21a	V22ª	V23	V24ª	V25ª	V26 EOT	Unscheduled	IP discontinuation (Section 7)	Follow-up ^b	
Week	R+4	R+8	R+12	R+16	R+20	R+24	R+28	-	4 weeks post-dose	8 weeks post-dose	
Visit Window (Days)	± 3	± 3	± 3	± 3	± 3	± 3	± 3		± 3	± 7	
General procedures											
Informed consent/assent	X	-	-	-	-	-	-	-	-	-	Appendix A 3
Return PRO device	X	-	-	-	-	-	-	-	-	-	8.2.1
Efficacy assessments						•	•				
Clinical Global Impression of Severity	X	X	X	X	X	X	X	-	X	-	8.1.5
Diet questionnaire	X	-	-	-	-	-	X	X	X	-	8.1.6
Healthcare resource utilization	X	-	-	-	-	-	X	-	X	-	8.8
Safety assessments						•					
Adverse events	X	X	X	X	X	X	X	X	X	X	8.3
Concomitant medication	X	X	X	X	X	X	X	X	X	X	6.5
Complete (brief) physical exam	-	-	-	-	-	-	X	(X)	X	-	8.2.1
Vital signs	-	-	-	-	-	-	X	X	X	-	8.2.2
Laboratory assessments					•						
Hematology/clinical chemistry	-	-	-	-	-	-	X	-	X	X	8.2.4
Urine pregnancy test ^c	-	-	-	-	-	-	X	-	X	X	8.2.5
Investigational product admini	stration				·	ı	ı	,			•
Administration	X	X d	X d	X	X d	X d	-	_	-	-	6.1.3

EOT: end of treatment; IP: investigational product. R: reference visit number of weeks (ie, number of weeks for the visit prior to approval of Amendment 4).

^a For patients who are self-administering IP, these visits can be conducted remotely by telephone contact.

Can be conducted remotely by telephone contact

^c Patients should be strongly encouraged to monitor for pregnancy during the study and report a pregnancy to the site as soon as possible.

d Optional at-home or remote location self-administration (Section 6.1.3.5).

Table 4 presents the schedule of activities for patient-reported outcomes prior to approval of Amendment 4. There will be no further collection of patient-reported outcome data following Visit 20 of Part D.

	During s	chedule	d clinic	visits		At home		CSP Section
	Run-in	Trea	tment p	eriod	Run-in, do	uble-blinded and	open-label	
Visit (V) (if applicable)	V1	V2	V8	V15				
Week ^a /Frequency	-8 to -4	0	24	52	Every evening from V1 until V20 ^b	Every 2 weeks from V1 until V20c	Every 4 weeks after V2 until V20c	
Symptom Assessment for Gastrointestinal Eosinophilic Diseases (SAGED)	-	-	-	-	X	-	-	8.1.3.1
Bristol Stool Form Scale	-	-	-	-	X	-	-	8.1.3.2

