7.1.2 Procedures for Early Discontinuation of Investigational Product

7.1.2.1 Early discontinuation of study treatment

All patients who prematurely discontinue IP should return to the study site for an IPD visit within 4 weeks (± 3 days) after the last dose of IP and an FU visit 4 weeks (± 7 days) after the last dose of IP for procedures described in Table 1 to Table 3. The IPD visit replaces the nearest scheduled visit after IP discontinuation. Patients will return the PRO device at the IPD visit if applicable. Patients who have discontinued IP during Part A are not eligible to enter Part C or Part D.

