7.1.3 Procedures for Handling Incorrectly Enrolled or Randomized Patients

Patients who fail to meet the eligibility criteria should not, under any circumstances, be randomized or receive IP. There can be no exceptions to this rule. Patients who are enrolled but who do not meet all eligibility criteria must not be randomized and must be withdrawn (screen failed) from the study.

When a patient does not meet all the eligibility criteria but is randomized in error or incorrectly started on IP, the Investigator should inform the AstraZeneca study physician immediately to discuss potential safety concerns and the best interests of the patient and decide whether IP should be continued or discontinued.

If the agreed decision is to discontinue IP, patients should be encouraged to complete IPD and FU visits, ie, follow-up for 4 weeks after last IP dose (if received) (Section 7.1.2).

The decision to discontinue/continue IP must be appropriately documented, including rationale, particularly if the agreed decision is to continue IP treatment.

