8 STUDY ASSESSMENTS AND PROCEDURES

- Study procedures and their timing are summarized in Table 1 to Table 3. Protocol waivers or exemptions are not allowed.
- The Investigator will ensure that data are recorded on the eCRF. The Web Based Data Capture (WBDC) system will be used for data collection and query handling.
- The Investigator ensures the accuracy, completeness, and timeliness of the data recorded and of the provision of answers to data queries according to the Clinical Study Agreement. The Investigator will sign the completed eCRF. A copy of the completed eCRF will be archived at the study site.
- Immediate safety concerns should be discussed with the sponsor immediately upon occurrence or awareness to determine if the participant should continue or discontinue study intervention.
- Adherence to the study design requirements, including those specified Table 1 to Table 3, is essential and required for study conduct.
- All screening evaluations must be completed and reviewed to confirm that potential
 participants meet all eligibility criteria. The investigator will maintain a screening log to
 record details of all participants screened and to confirm eligibility or record reasons for
 screening failure, as applicable.
- Procedures conducted as part of the participant's routine clinical management (eg, blood count) and obtained before signing of the ICF may be utilized for screening or baseline purposes provided the procedures met the protocol-specified criteria and were performed within the time frame defined in Table 1 to Table 3.

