8.3.1 Time Period and Frequency for Collecting AE and SAE Information

AEs will be collected from time of signature of the IFC throughout the treatment period and including the follow-up period.

SAEs will be recorded from the time of signing of the IFC.

All SAEs will be recorded and reported to the Sponsor or designee within 24 hours, as indicated in Appendix B. The Investigator will submit any updated SAE data to the Sponsor within 24 hours of it being available.

If the investigator becomes aware of an SAE with a suspected causal relationship to the investigational medicinal product that occurs after the end of the clinical study in a participant treated by him or her, the investigator shall, without undue delay, report the SAE to the sponsor.

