# 4.6.2 Adverse Events

#### 4.6.2.1 Definitions and Derivations

Adverse events experienced by the patients will be collected throughout the entire study and will be coded using the latest version of the Medical Dictionary for Regulatory Activities (MedDRA) per the Data Management Plan.

Adverse event data will be categorized according to their onset date into the following study periods:

- AEs in the pre-treatment period are defined as those with onset day before day of first dose of study treatment.
- AEs in the on-treatment period are defined as those with onset day between day of first dose of study treatment and scheduled end of treatment (EOT) visit for patients who complete study treatment or investigational product discontinuation visit (IPD) for patients who prematurely discontinue study treatment, inclusive. In the event that the EOT or IPD visit is beyond the protocol-defined visit window, AEs with onset after the last dose of study treatment date +28 days +3 days (visit window) will be excluded from the on-treatment period and instead assigned to the post-treatment period.
- AEs in the on-study period are defined as those with onset between day of first dose of study treatment and the day of the scheduled follow-up visit, inclusive.
- AEs in the post-treatment period are defined as those with onset after the ontreatment period defined above.

- On-study AEs in the DB period will be defined as those with onset date between day of first dose of study DB treatment and the day prior to the first dose of OLE period (up to and including day of V9 for patients who do not roll over to OLE).
- On-study AEs in the OLE period are defined as those with onset date on or after the day of the first dose of OLE treatment and up to EOT.

For instances where a patient attends the safety follow-up visit only, but does not attend an earlier IPD visit or EOT visit, adverse events occurring on or after the day of first dose of study treatment and on or before the last dose of study medication + 28 days will be assigned to the on-treatment period, while AEs with onset date after this time will be assigned to the post-treatment period.

If an AE has a missing onset date it will be considered an on-treatment event unless the stop date of the AE indicates otherwise. Similarly, if an AE has a partial onset date it will be considered an on-treatment AE unless the partial onset date or the stop date indicates otherwise.

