#### 8 ADDENDUM

Protocol Version 5 (Amendment 4) was issued on March 28, 2023, after the decision to close recruitment to the study early. The amendment rationale was to fulfil a commitment to participants, from when they enrolled in the trial, of open-label access to benrazilumab following double-blind treatment.

Patients that completed Part A prior to approval of amendment 4 could choose to continue to Part C, an extended open-label benralizumab treatment period. Patients in Part A and Part C, after protocol amendment approval in their respective country, will be given the option at their next clinic visit of withdrawing from the study or moving on to Part D and receiving 6 months of open-label benralizumab Q4W dosing. Patients will not complete their current treatment period. Patients who have discontinued IP during Part A are not eligible to enter Part C or D.

Enrollment was terminated after enrollment of 34 participants, of which 12 were randomized. The figure below illustrates the current study design described above.

Figure 4 Study Design Flow Chart

Q4W: every fourth week; R: reference visit number of weeks (ie, visit prior to approval of Amendment 4); EoT: end of treatment; FU: follow-up.

Given the original sample size of the study will no longer be recruited and the study will be terminated, the analysis plan for the study was updated. The amended analysis plan will now consist of descriptive summaries of safety data and select patient listings of baseline characteristics, safety data, and key efficacy data for the double-blind placebo-controlled period (part A) and the open-label period (Parts C and D). Details on the descriptive summaries can be found below in Table 11.

Principles outlined in the main SAP document related to these descriptive summaries below will apply i.e. definition of periods for safety summaries. Other analyses described in the main SAP will no longer be implemented given the small final sample size limiting the ability to assess the original study objectives.

Table 11 List of summaries for the final analyses

Summaries	Period Period	Population	Format
Subject disposition	DB + OLE	All patients analysis set	Table
Duration of exposure	DB	Safety analysis set	Table
Duration of exposure	OLE	Open-label benralizumab analysis set	Table
Adverse events in any category	DB	Safety analysis set	Table
Adverse events in any category	OLE	Open-label benralizumab analysis set	Table

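### The protocol text puts the follow-up visit after early discontinuation at 4 weeks after the last dose, the visit tables put it at 8 weeks, and no date satisfies both

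*Protocol*

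**What the plan says.** Protocol 7.1.2.1 requires two visits after early IP discontinuation. The first is an IP discontinuation (IPD) visit within 4 weeks (±3 days) of the last dose. The second is "an FU visit 4 weeks (± 7 days) after the last dose of IP for procedures described in Table 1 to Table 3".

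Protocol 7.1.3, on patients enrolled or randomized in error, encourages those taken off IP to complete the IPD and FU visits. It glosses this as "follow-up for 4 weeks after last IP dose (if received" and cross-refers to 7.1.2.

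The Schedule of Activities in Protocol 1.3 differs. The Follow-up column reads "8 weeks post- dose" in Table 1 (Part A) and in Table 2 (Part C), and "8 weeks post-dose" in Table 3 (Part D). Each has a ±7 day window. All three tables put the IPD visit at 4 weeks ±3 days, in its own column.

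On AE collection, Protocol 8.3.1 states: "AEs will be collected from time of signature of the IFC throughout the treatment period and including the follow-up period". SAP 4.6.2.1 defines a general on-study AE period by "onset between day of first dose of study treatment and the day of the scheduled follow-up visit, inclusive". The SAP addendum adds: "Principles outlined in the main SAP document related to these descriptive summaries below will apply i.e. definition of periods for safety summaries".

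**The concern.** Section 7.1.2.1 is where a site will look when a patient stops drug early. It gives one date for the FU visit and then refers the site to tables that give another. Whichever date the site picks, it departs from one protocol instruction.

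What is at stake is safety observation after the last dose. Dosing is every 4 weeks, so day 28 is when the next injection would have been due. A follow-up visit on that day gives essentially no observation beyond one dosing interval. Because AE collection runs through the follow-up period, a site using the 4-week date could stop routine collection there. It would also do the second haematology, chemistry and pregnancy checks at about the time of the tables' IPD checks. The patients concerned include those stopped for an AE, an anaphylactic reaction or hepatitis B reactivation (Protocol 7.1.1), for whom later safety data matter most.

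**Working it through.** The plan states no figure that needs reproducing. The check is day arithmetic and a comparison of texts.

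**Inputs, in days after the last dose (weeks × 7 ± window)**
- FU, text (7.1.2.1): 4 × 7 ± 7 = 28 ± 7, so days 21 to 35.
- FU, tables (Tables 1, 2 and 3): 8 × 7 ± 7 = 56 ± 7, so days 49 to 63.
- IPD, tables: 4 × 7 ± 3 = 28 ± 3, so days 25 to 31.
- Section 7.1.3 gives 4 weeks with no window: day 28, also outside days 49 to 63.

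**Overlap of the two FU windows**
- The latest text date is day 35 and the earliest table date is day 49.
- 49 − 35 = 14 days, so the windows do not meet.

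**Difference in FU date**
- Nominal: 56 − 28 = 28 days.
- Smallest: 49 − 35 = 14 days. Largest: 63 − 21 = 42 days.

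**Shared nominal day**
- Day 28 is both the text's FU day and the tables' IPD day, although both sources treat IPD and FU as separate visits.

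**After correction to 8 weeks (±7 days)**
- FU falls on days 49 to 63. Measured from the tables' IPD window it comes 49 − 31 = 18 to 63 − 25 = 38 days later, nominally 28.

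**Does the FU date set a cut-off in the retained AE tables?**
- SAP Table 11 keeps AE tables labelled by double-blind (DB) and open-label (OLE) period.
- SAP 4.6.2.1 has AE definitions specific to those periods. DB on-study AEs run to the day before the first OLE dose, or through V9 for patients who do not roll over. OLE on-study AEs run to the end-of-treatment visit.
- Neither definition ends at the FU visit. Only the general on-study period does.
- Table 11 also keeps an AE listing for DB and OLE on the safety analysis set. Its content depends on what was collected.

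**The case against.** The strongest reply is that sites will probably use 8 weeks anyway. The three tables agree with one another. Sections 7.1.1 and 7.2 send sites to them for what to collect at discontinuation, withdrawal and follow-up, and section 8 says: "Adherence to the study design requirements, including those specified Table 1 to Table 3, is essential and required for study conduct". Section 7.1.3 is not an independent rule, since it borrows its figure from 7.1.2. All of this stands. It makes harm less likely, but it does not remove the contradictory instruction.

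The 4 weeks could also be read as counted from the IPD visit, which would land near week 8. Both sections, however, count from the last dose. Nor is the Table 1 footnote with a 12-week FU visit a third value for the same visit: it covers patients who complete Part A and choose not to enter Part C.

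Several stronger inferences are tempting but not supported:
- **That the retained AE summary tables would be cut short.** The general on-study period and the addendum's sentence might suggest this. The DB- and OLE-specific definitions do not end at FU. SAP 3.3.1.1 defines the study periods more broadly, so a zero effect cannot be claimed. An event never recorded is also missing from any output it would have entered. That is a loss through collection, not a cut-off set by the FU date.
- **That the two visits must coincide under the text.** Section 7.1.2.1 places IPD within 4 weeks, which can be read as any day up to about day 31. Only the shared nominal day with the tables' IPD visit is certain.
- **That all late safety information would be lost.** Suspected-related SAEs stay reportable after the study (8.3.1). Unresolved AEs are still followed clinically, without eCRF recording (8.3.2). Pregnancy outcomes are still followed (8.3.9.1).
- **That a second set of laboratory samples is assured at week 8.** A Table 3 footnote allows the Part D follow-up to be by telephone, although the column marks laboratory and pregnancy tests.

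**Conclusion.** The contradiction is real and lies in current operative text. The FU windows are days 21 to 35 and days 49 to 63, 14 days apart, with nominal dates 28 days apart. Eight weeks is the value to keep: all three tables give it, and it leaves a clear interval after the tables' IPD visit.

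The consequence is modest. If a site followed the text, what could go unrecorded is mainly new-onset AEs between about weeks 4 and 8 that are non-serious or not suspected to be related. The effect falls on AE collection and the AE listing, not on the period definitions behind the retained DB and OLE tables. This rests on two assumptions: that some patients stop early, and that their site uses the text. The documents give no number stopping early, and at most the 12 randomized patients are concerned. No hypothesis test is planned, so no inferential result is at risk. The correction should be made, but the point does not cast doubt on the analysis.

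**What to change.** In Protocol 7.1.2.1, set the FU visit at 8 weeks (±7 days) after the last dose of IP. In Protocol 7.1.3, change the 4 weeks of follow-up to 8 weeks. Leave Tables 1 to 3 as they are, and leave the Table 1 footnote, which addresses a different group. The SAP needs no change.

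The cost is one number in each of two sections, with no new visit, procedure or analysis. A site already working from the tables would notice no difference.

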7.1.3 Procedures for Handling Incorrectly Enrolled or Randomized Patients

Patients who fail to meet the eligibility criteria should not, under any circumstances, be randomized or receive IP. There can be no exceptions to this rule. Patients who are enrolled but who do not meet all eligibility criteria must not be randomized and must be withdrawn (screen failed) from the study.

When a patient does not meet all the eligibility criteria but is randomized in error or incorrectly started on IP, the Investigator should inform the AstraZeneca study physician immediately to discuss potential safety concerns and the best interests of the patient and decide whether IP should be continued or discontinued.

If the agreed decision is to discontinue IP, patients should be encouraged to complete IPD and FU visits, ie, follow-up for 4 weeks after last IP dose (if received) (Section 7.1.2).

The decision to discontinue/continue IP must be appropriately documented, including rationale, particularly if the agreed decision is to continue IP treatment.

7.2 Participant Withdrawal from the Study

- A participant may withdraw from the study at any time at his/her own request or may be withdrawn at any time at the discretion of the investigator for safety, behavioral, compliance, or administrative reasons. This is expected to be uncommon.
- At the time of withdrawal from the study, if possible, an IP Discontinuation visit should be conducted, as shown in the schedule of activities. See Table 1 to Table 3 for what to be collected at the time of study withdrawal and follow-up and for any further evaluations that need to be completed.
 - The participant will discontinue the study intervention and be withdrawn from the study at that time.
 - Endoscopy should be performed at the discretion of the Sponsor and only if ≥12 weeks have elapsed since the prior endoscopy.
- If the participant withdraws consent for disclosure of future information, the sponsor may retain and continue to use any data collected before such a withdrawal of consent.
- If a participant withdraws from the study, it should be confirmed if he/she still agrees for existing samples to be used in line with the original consent. If he/she requests withdrawal of consent for use of samples, destruction of any samples taken and not tested should be carried out in line with what was stated in the ICF and local regulations. The investigator must document the decision on use of existing samples in the site study records and inform the Global Study Team.

